9.7.1 Sample Size

Adverse Event						
Frequency	N = 20					
0.01%	0.20					
Rare	0.20					
0.1%	1.09					
Uncommon	1.98					
1%	10.21					
Common	18.21					
10%	97.94					
Very Common	87.84					
20%						
Very Common	98.85					

Table 2: Probability (%) of Observing at Least One Adverse Event

10.2 Protocol Deviations

Table 3: Distribution of Protocol Deviations by Category, Type, and Treatment Group

		HEV (N=	/-239 =X)	Plac (N=	cebo =X)	All Subjects (N=X)		
Category	Deviation Type	No. of Subj.	No. of Dev.	No. of Subj.	No. of Dev.	No. of Subj.	No. of Dev.	
Eligibility/enrollment	Any type							
	Did not meet inclusion criterion	х	х	х	х	х	х	
	Met exclusion criterion							
	ICF not signed prior to study procedures							
	Other							
Treatment administration schedule	Any type							
	Out of window visit							
	Missed visit/visit not conducted							
	Missed treatment administration							
	Delayed treatment administration							
	Other							
Follow-up visit schedule	Any type							
	Out of window visit							
	Missed visit/visit not conducted							
	Other							
Protocol procedure/assessment	Any type							
	Incorrect version of ICF signed							
	Blood not collected							
	Urine not collected							
	Stool not collected							
	Other specimen not collected							
	Too few aliquots obtained							
	Specimen result not obtained							
	Required procedure not conducted							
	Required procedure done incorrectly							
	Study product temperature excursion							
	Specimen temperature excursion							
	Other							
Treatment administration	Any type							
	Required procedure done incorrectly							
	Study product temperature excursion							
	Other							
Blinding policy/procedure	Any type							
	Treatment unblinded							
	Other							

Note: N= Number of subjects enrolled

12.2.2 Displays of Adverse Events

Table 4: Solicited Adverse Event Grading Scale – Local (Injection Site) Reactogenicity Grading

Local (Injection Site) Reaction	Mild (Grade 1)	Moderate (Grade 2)	Severe (Grade 3)
Pain – experienced without touching the injection site (spontaneous discomfort)	No pain medication or it requires use of a non-narcotic pain reliever ≤24hours OR does not interfere with activity	Repeated use of non-narcotic pain reliever >24 hours OR interferes with activity	Any use of narcotic pain reliever OR prevents daily activity
Tenderness – hurts only when injection site is touched or the arm is moved	Discomfort only to touch	Discomfort with movement	Significant discomfort at rest
Pruritus (Itching)	Does not interfere with daily activity	Interferes with daily activity	Prevents daily activity
Ecchymosis (Bruising) Severity ^a	Does not interfere with daily activity	Interferes with daily activity	Prevents daily activity
Induration (Hardness)/Swelling Severity ^a	Does not interfere with daily activity	Interferes with daily activity	Prevents daily activity
Ecchymosis (Bruising) Measurement ^b	25mm – 50mm	51 mm – 100mm	>100 mm
Erythema (Redness) Measurement ^b	25 mm – 50 mm	51 mm – 100 mm	>100 mm
Induration (Hardness)/Swelling Measurement ^b	25 mm – 50 mm	51 mm – 100 mm OR interferes with activity	>100 mm OR prevents daily activity

^a Will also be measured in mm but size will not be used as halting criteria.

^b Will not be used as halting criteria.

Systemic	Mild (Grade 1)	Moderate (Grade 2)	Severe (Grade 3)
Feverishness (Chills/Shivering/Sweating)	No interference with daily activity	Some interference with daily activity	Significant interference, prevents daily activity
Fatigue (Tiredness)	No interference with daily activity	Some interference with daily activity	Significant interference, prevents daily activity
Malaise (General Unwell Feeling)	No interference with daily activity	Some interference with daily activity	Significant interference, prevents daily activity
Myalgia (Body Aches/Muscular Pain) ^a	No interference with daily activity	Some interference with daily activity	Significant interference, prevents daily activity
Arthralgia (Joint Pain) ^a	No interference with daily activity	Some interference with daily activity	Significant interference, prevents daily activity
Headache	No interference with daily activity	Repeated use of non-narcotic pain reliever >24 hours OR some interference with activity	Significant; any use of narcotic pain reliever OR prevents daily activity OR requires triptans
Nausea	No interference with daily activity	Some interference with daily activity	Significant interference, prevents daily activity
Vomiting	No interference with activity or 1-2 episodes/24 hours	Some interference with activity or >2 episodes/24 hours	Prevents daily activity or requires IV hydration
Fever ^b – oral	38.0°C – 38.4°C 100.4°F – 101.1°F	38.5°C – 38.9°C 101.2°F – 102.0°F	>38.9°C >102.0°F

Solicited Adverse Event Grading Scale – Systemic Reactogenicity Grading Table 5:

^a Not at injection site. ^b A fever can be considered not related to the study product if an alternative etiology can be documented

12.4.1 Individual Laboratory Measurements and Abnormal Laboratory Values

Table 6:Laboratory Adverse Event Grading Scale

Laboratory Adverse Events							
Blood, Serum, or Plasma	Normal Range	Mild (Grade 1)	Moderate (Grade 2)	Severe (Grade 3)			
Creatinine – mg/dL (Female)	0.5 - 1.10	≥1.11 – 1.79	≥1.80-2.09	≥2.10			
Creatinine – mg/dL (Male)	0.6 - 1.35	≥1.36 – 1.79	≥1.80-2.09	≥2.10			
ALT U/L (Female)	6 – 29	30 - 105	106-175	>175			
ALT U/L (Male)	9 - 46	47 - 105	106-175	>175			
Hemoglobin (Female) - g/dL	11.7 – 15.5	11.0-11.6	9.5-10.9	<9.5			
Hemoglobin (Male) - g/dL	13.2 - 17.1	12.0 - 13.1	10.0 - 11.9	<10.0			
WBC Increase (Thousand/uL)	3.8 - 10.8	10.9 - 15.0	15.1 - 20.0	> 20.0			
WBC Decrease (Thousand/uL)	3.8 - 10.8	2.5-3.7	1.5-2.4	<1.5			
Absolute Neutrophil Count Decrease (cells/uL)	1500 - 7800	1490 - 1499	1000-1489	<1000			
Absolute Eosinophil Count Increase (cells/uL)	15 - 500	501-749	750-1500	>1500			
Platelets Decreased (Thousand/uL)	140 - 400	120-139	100-119	<100			

Table 7.	Vital Signs	Adverse	Event	Grading	Scale
I abic /.	v Ital Signs	Auveise	LVCIII	Grauing	Scale

Vital Sign	Mild (Grade 1)	Moderate (Grade 2)	Severe (Grade 3)
Fever (°C) ¹	38.0 - 38.4	38.5 - 38.9	≥39.0
Tachycardia - beats per minute	101 – 115	116 - 130	>130 or ventricular dysrhythmias
Bradycardia - beats per minute	45 - 50 bpm	40 – 44 bpm	<40 bpm
Hypertension (systolic)- mm Hg ²	141-150	151-160	>160
Hypertension (diastolic) - mm Hg ²	91-95	96-100	>100
Hypotension (systolic) - mm Hg ²	85-89	80-84	< 80
Hypotension (diastolic) – mm Hg ²	50 - 54	45 - 49	<45

¹ Oral temperature; no recent hot or cold beverages or smoking. ² Assuming subject is awake, and resting for AEs; 3 measurements on the same arm with concordant results.

Description of Study Subjects 14.1

14.1.1 Disposition of Subjects

Subject Disposition by Treatment Group Table 8:

Subject	HEV-239 (N=X)		Placebo (N=X)		All Subjects (N=X)	
Disposition	n	%	n	%	n	%
Screened					Х	
Enrolled/Randomized	х	100	х	100	х	100
Received Dose 1	Х	XX	х	XX	Х	XX
Received Dose 2	Х	XX	х	XX	Х	XX
Received Dose 3	Х	XX	х	XX	Х	XX
Completed Final Blood Draw						
Completed Follow-up (Study Day 360) ^a						
Completed Per Protocol ^b						

Note: N=All subjects

^a Refer to Listing 16.2.1 for reasons subjects discontinued or terminated early.
 ^b Refer to Listing 16.2.3 for reasons subjects are excluded from the Analysis populations.

		HEV-239 (N=X)		Placebo (N=X)		All Subjects (N=X)	
Analysis Populations	Reason Subjects Excluded	n	%	n	%	%	n
Safety Population	Any Reason	х	XX	х	xx	х	xx
	Did not receive study product						
Modified Intent-to-Treat Population	Any Reason						
	No pre-vaccination serum results						
	No post-vaccination serum results						
Per Protocol Population	Any Reason						
	Ineligible at baseline						
	Did not receive all 3 doses						
	Received non-study licensed vaccine						
	Received immunosuppressive therapy						

Table 9: Analysis Populations by Treatment Group

Note: N=All subjects enrolled

Table 10: Dates of First Treatment by Treatment Group

Dates of Dosing	HEV-239 (N=X)	Placebo (N=X)	All Subjects (N=X)
Total (Entire period of enrollment)			
DDMMMYYYY-DDMMMYYYY [categorize based on length of enrollment period]	Х	X	Х

Note: N=Number of subjects in the Safety Population

Inclusion/Exclusion Category	Inclusion/Exclusion Criterion	n ^a	% ^b
Inclusion and Exclusion	Number of subjects failing any eligibility criterion	х	XX
Inclusion	Any inclusion criterion	х	XX
	[inclusion criterion 1]	х	XX
	[inclusion criterion 2]	х	XX
	[inclusion criterion 3]	х	XX
Exclusion	Any exclusion criterion	х	XX
	[exclusion criterion 1]	х	XX
	[exclusion criterion 2]	х	XX
	[exclusion criterion 3]	х	XX
Eligible but not enrolled		Х	XX

Table 11: **Ineligibility Summary of Screen Failures**

^a More than one criterion may be marked per subject. ^b Denominator for percentages is the total number of screen failures.

14.1.2 Demographic Data by Study Group

Table 12: Summary of Categorical Demographic and Baseline Characteristics

		HEV-239 (N=X)		Placebo (N=X)		All Subjects (N=X)	
Variable	Characteristic	n	%	n	%	n	%
Sex	Male	х	XX	х	xx	х	XX
	Female						
Ethnicity	Not Hispanic or Latino	х	XX	х	xx	х	XX
	Hispanic or Latino						
	Not Reported						
	Unknown						
Race	American Indian or Alaska Native	х	XX	х	xx	х	xx
	Asian						
	Native Hawaiian or Other Pacific Islander						
	Black or African American						
	White						
	Multi-Racial						
	Unknown						

Note: N=Number of subjects in the Safety Population

Table 13: S	Summary of Cor	tinuous Demogra	phic and Baseline	Characteristics
-------------	----------------	-----------------	-------------------	-----------------

Variable	Statistic	HEV-239 (N=X)	Placebo (N=X)	All Subjects (N=X)
Age (years)	Mean	XX	XX	XX
	Standard Deviation	XX	XX	XX
	Median	Х	Х	Х
	Minimum	Х	Х	Х
	Maximum	Х	х	Х

Note: N=Number of subjects in the Safety Population

14.1.3 Prior and Concurrent Medical Conditions

Table 14:Summary of Subjects with Pre-Existing Medical Conditions by MedDRA System Organ
Class and Treatment Group

	HEV-239 (N=X)		Placebo (N=X)		All Subjects (N=X)	
MedDRA System Organ Class	n	%	n	%	n	%
Any SOC	х	XX	х	XX	х	XX
[SOC 1]						
[SOC 2]						

Note: N=Number of subjects in the Safety Population; n = Number of subjects reporting medical history within the specified SOC. A subject is only counted once per SOC.

14.2 Immunogenicity Data

Table 15:Serum HEV IgG GMC Results with 95% Confidence Intervals by Time Point and
Treatment Group, mITT Population

Time Point	Statistic	HEV-239 (N=X)	Placebo (N=X)
Day 1 (Dose 1)	n	X	Х
	GMC	X.X	X.X
	95% CI	x.x, x.x	x.x, x.x
	[Min, Max]	[x.x, x.x]	[x.x, x.x]
Day 8	n		
	GMC		
	95% CI		
	[Min, Max]		
Day 15	n		
	GMC		
	95% CI		
	[Min, Max]		
Day 29 (Dose 2)	n		
	GMC		
	95% CI		
	[Min, Max]		
Day 36	n		
	GMC		
	95% CI		
	[Min, Max]		
Day 43	n		
	GMC		
	95% CI		
	[Min, Max]		
Day 57	n		
	GMC		
	95% CI		
	[Min, Max]		
Day 180 (Dose 3)	n		
	GMC		
	95% CI		
	[Min, Max]		
Day 187	n		

Time Point	Statistic	HEV-239 (N=X)	Placebo (N=X)
	GMC		
	95% CI		
	[Min, Max]		
Day 194	n		
	GMC		
	95% CI		
	[Min, Max]		
Day 208	n		
	GMC		
	95% CI		
	[Min, Max]		
Day 360	n		
	GMC		
	95% CI		
	[Min, Max]		

Note: N= Number of subjects in the mITT Population; n=Subjects with results at visit

Tables with similar format:

- Table 16:Serum HEV IgG GMC Results with 95% Confidence Intervals by Time Point and
Treatment Group, Per Protocol Population
- Table 17:Serum HEV IgM GMC Results with 95% Confidence Intervals by Time Point and
Treatment Group, Per Protocol Population
- Table 18:Serum HEV IgM GMC Results with 95% Confidence Intervals by Time Point and
Treatment Group, Per Protocol Population

Time Point	Statistic	HEV-239 (N=X)	Placebo (N=X)
Day 8	n	X	Х
	GMFR ^a	X.X	X.X
	95% CI	X.X, X.X	X.X, X.X
	4-Fold Rise ^b	X.X	X.X
	95% CI	X.X, X.X	X.X, X.X
Day 15	n		
	GMFR ^a		
	95% CI		
	4-Fold Rise ^b		
	95% CI		
Day 29 (Dose 2)	n		
	GMFR ^a		
	95% CI		
	4-Fold Rise ^b		
	95% CI		
Day 36	n		
	GMFR ^a		
	95% CI		
	4-Fold Rise ^b		
	95% CI		
Day 43	n		
	GMFR ^a		
	95% CI		
	4-Fold Rise ^b		
	95% CI		
Day 57	n		
	GMFR ^a		
	95% CI		
	4-Fold Rise ^b		
	95% CI		
Day 180 (Dose 3)	n		
	GMFR ^a		
	95% CI		
	4-Fold Rise ^b		

Table 19:Serum HEV IgG GMFR and Seroresponse (4-Fold Rise)
Results by Time Point and Treatment Group, mITT Population

Time Point	Statistic	HEV-239 (N=X)	Placebo (N=X)
	95% CI		
Day 187	n		
	GMFR ^a		
	95% CI		
	4-Fold Rise ^b		
	95% CI		
Day 194	n		
	GMFR ^a		
	95% CI		
	4-Fold Rise ^b		
	95% CI		
Day 208	n		
	GMFR ^a		
	95% CI		
	4-Fold Rise ^b		
	95% CI		
Day 360	n		
	GMFR ^a		
	95% CI		
	4-Fold Rise ^b		
	95% CI		

Note: N=Number of subjects in the mITT Population; n=Subjects with results at visit

^a GMFR represents the geometric mean fold rise in antibody compared to pre-dose 1.

^b 4-Fold Rise represents the percentage of subjects with at least a 4-Fold Rise in antibody compared to pre-dose 1.

Tables with similar format:

Table 20:Serum HEV IgG GMFR and Seroresponse (4-Fold Rise)Results by Time Point and Treatment Group, Per Protocol Population

Table 21:Serum HEV IgM GMFR and Seroconversion Results by Time Point and Treatment
Group, mITT Population

Time Point	Statistic	HEV-239 (N=X)	Placebo (N=X)
Day 8	n	Х	Х
	GMFR ^a	X.X	X.X
	95% CI	x.x, x.x	x.x, x.x
	Seroconversion ^b	X.X	X.X
	95% CI	x.x, x.x	X.X, X.X
Day 15	n		
	GMFR ^a		
	95% CI		
	Seroconversion ^b		
	95% CI		
Day 29 (Dose 2)	n		
	GMFR ^a		
	95% CI		
	Seroconversion ^b		
	95% CI		
Day 36	n		
	GMFR ^a		
	95% CI		
	Seroconversion ^b		
	95% CI		
Day 43	n		
	GMFR ^a		
	95% CI		
	Seroconversion ^b		
	95% CI		
Day 57	n		
	GMFR ^a		
	95% CI		
	Seroconversion ^b		
	95% CI		
Day 180 (Dose 3)	n		
	GMFR ^a		
	95% CI		
	Seroconversion ^b		
	95% CI		

Time Point	Statistic	HEV-239 (N=X)	Placebo (N=X)
Day 187	n		
	GMFR ^a		
	95% CI		
	Seroconversion ^b		
	95% CI		
Day 194	n		
	GMFR ^a		
	95% CI		
	Seroconversion ^b		
	95% CI		
Day 208	n		
	GMFR ^a		
	95% CI		
	Seroconversion ^b		
	95% CI		
Day 360	n		
	GMFR ^a		
	95% CI		
	Seroconversion ^b		
	95% CI		

Note: N=Number of subjects in the mITT Population; n=Subjects with results at visit

^a GMFR represents the geometric mean fold rise in antibody compared to pre-dose 1.

^b Seroconversion represents the percentage of subjects with a change from a seronegative result at pre-dose 1 to a seropositive result.

Tables with similar format:

Table 22:Serum HEV IgM GMFR and Seroconversion Results by Time Point and Treatment
Group, Per Protocol Population

Time Point	Statistic	HEV-239 (N=X)	Placebo (N=X)
Day 8	n	X	X
	Seroconversion ^a	X.X	X.X
	95% CI	x.x, x.x	X.X, X.X
Day 15	n		
	Seroconversion ^a		
	95% CI		
Day 29 (Dose 2)	n		
	Seroconversion ^a		
	95% CI		
Day 36	n		
	Seroconversion ^a		
	95% CI		
Day 43	n		
	Seroconversion ^a		
	95% CI		
Day 57	n		
	Seroconversion ^a		
	95% CI		
Day 180 (Dose 3)	n		
	Seroconversion ^a		
	95% CI		
Day 187	n		
	Seroconversion ^a		
	95% CI		
Day 194	n		
	Seroconversion ^a		
	95% CI		
Day 208	n		
	Seroconversion ^a		
	95% CI		
Day 360	n		
	Seroconversion ^a		
	95% CI		

Table 23:Serum HEV IgG Seroconversion Results by Time Point and Treatment Group, mITT
Population

Note: N=Number of subjects in the mITT Population; n=Subjects with results at visit

^a Seroconversion represents the percentage of subjects with a change from a seronegative result at pre-dose 1 to a seropositive result.

Tables with similar format:

Table 24:Serum HEV IgG Seroconversion Results by Time Point and Treatment Group, Per
Protocol Population

Safety Data 14.3

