5.1 Eligibility Criteria

Screening for eligible subjects must be performed within 28 days before Day 1. The investigator should ensure that all study enrollment criteria have been met at the end of the screening period. If a subject's status changes (including laboratory results or the receipt of additional medical records) after screening but before the prime vaccination such that the subject no longer meets all eligibility criteria, then the subject should be excluded from participation in the study.

Enrollment will be based solely on the eligibility criteria outlined below and will be open to both sexes and all races/ethnicities. Sex and minority breakdown cannot be predicted for this study but should follow the general population distribution. Pregnant women and women who are breastfeeding will not be eligible for inclusion.

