6.2 Enrollment/Baseline: Visit 01, Day 1, Vaccination Clinic Visit (All Groups)

The investigator should ensure that all enrollment criteria have been met during screening. If a subject's status (including any unscheduled laboratory results or the receipt of additional medical records) after screening but before the prime vaccination changes such that the subject no longer meets all enrollment criteria, then the subject should be excluded from participation in the study.

If the initial laboratory screening occurred more than 28 days before baseline (Day 1) but the subject was unable to be vaccinated within the 28-day window (e.g., due to meeting **Exclusion Criteria** in **Section 5.1.2** or for other reasons), the subject must have safety laboratories repeated (see protocol-specific MOP for details about laboratories).

Prior to Vaccination

- Review inclusion and exclusion criteria to ensure the subject remains eligible for enrollment
- Review medical history for any interval changes
- Review prestudy and concomitant medications
- Obtain vital signs (HR, BP, and oral temperature)
- Subjects who have a diastolic blood pressure value >90 mmHg or a systolic blood pressure value >140 mmHg prior to the prime vaccination can receive the vaccination if the elevated blood pressure is considered to be not clinically significant and the subject had acceptable blood pressure at screening.

- Perform symptom-directed PE (if needed).
- Perform urine pregnancy test for women of childbearing potential within 24 hours prior to immunization. Test result must be known and negative prior to vaccination.
- Review of birth control history with female subjects
- Counsel subjects to use adequate birth control methods to avoid pregnancy
- Subjects will be enrolled in Advantage eClinical[®] and randomly assigned to a Study Group (see Section 10.3.1 Randomization Procedures for details).
- Obtain serum for immunogenicity assays.
- Collect PBMCs and plasma for future assays.
- Study vaccine will be prepared on-site by an unblinded site research pharmacist (see Section 4.3).
- Pre-administration reactogenicity assessments will be performed prior to the first study vaccination to establish baseline. A subject with mild pre-administration reactogenicity which is transient, resolving, or clinically insignificant may receive vaccination at the investigator's discretion.

Vaccination

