10 STATISTICAL CONSIDERATIONS

10.1 Study Hypotheses

The primary goal of this study is to assess the safety and immunogenicity of HEV 239 administered in three successive intramuscular injections. This study will also collect blood for future use. This study, like other Phase I studies, is exploratory rather than confirmatory, and thus is not designed to formally test any hypotheses.

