3.3. Study Definitions and Derived Variables

The baseline value will be defined as the last value obtained prior to the first vaccination/dose of study product.

Seronegative samples will be defined as per the Wantai HEV-IgM and IgG ELISA package inserts (Absorbance Value / Cut-Off Value (A/C.O.) <0.9).

Seroconversion will be defined as a change from a seronegative result to a seropositive result as defined by the Wantai HEV-IgM and IgG ELISA package inserts (A/C.O. >1.1). Samples with borderline A/C.O. values (0.9-1.1) will be retested in duplicate. If both retests are negative (as defined above), the result will be reported as negative. If one or both retests are positive, the result will be reported as positive. If both retest values are in the borderline zone, the result will be reported as indeterminant.

A 4-fold seroconversion will be defined as a HEV IgG ≥ 0.154 in a subject that was HEV seronegative at baseline.

Duration of solicited events will be defined as the number of contiguous symptomatic days.

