4.5.2. Immunogenicity Variables

Assays to determine serum levels of hepatitis E antibodies (IgG and IgM) will be performed at Emory's VTEU laboratory. Venous blood samples (approximately 10 mL) for antibody assays will be collected from each subject at screening and sent directly to Emory's VTEU laboratory for baseline testing. Seronegative samples will be defined as per the Wantai HEV-IgM and IgG ELISA package inserts (A/C.O. <0.9).

Venous blood samples (approximately 10 mL) will be collected immediately prior to each study vaccination (Days 1, 29, and 180) and Days 8, 15, after each study vaccination (Days 8, 15, 36, 43, 187, 194), Day 29 after each boost vaccination (Days 57 and 208), and Day 360. Subjects who withdraw early will have hepatitis E antibody assays run on available sera. Samples for immunogenicity assessments will be shipped from the DMID CMS to Emory's VTEU laboratory for vaccine immunogenicity assessments beginning with the completion of the Day 360 visit.

Seroconversion will be defined as a change from a seronegative result to a seropositive result as defined by the Wantai HEV-IgM and IgG ELISA package inserts (A/C.O. >1.1). As defined by prior studies,²⁴ the antibody concentration in samples negative for hepatitis E virus IgG was set at 0.0385 Wu/mL which was half the lower limit of quantification. A 4-fold seroconversion will be defined as a HEV IgG \geq 0.154 in a subject that was HEV seronegative at Day 1.

Immunogenicity will be assessed by serum immune responses:

• Serum will be separated from blood samples collected on Days 1, 8, 15, 29, 36, 43, 57, 180, 187, 194, 208, and 360 and HEV IgG and IgM will be determined by ELISA.

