5. SAMPLE SIZE CONSIDERATIONS

The sample size for this study was selected to obtain preliminary estimates of HEV-239 vaccine safety and immunogenicity in a time sensitive manner.

Given an N of 20 vaccinees, there is an \sim 88% probability of detecting an adverse event occurring in 10% of the population and a \sim 99% probability of detecting an adverse event occurring in 20%. Placebo subjects are included in order to reduce observer bias and are not intended to be a comparison group. Probabilities of observing at least one adverse event for a given true event rate are presented in the Table 2.

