8.1. Primary Immunogenicity Analysis

HEV IgG by ELISA

The number and percentage of subjects showing \geq 4-fold rise from the baseline in serum HEV IgG concentration determined by ELISA will be presented with exact (Clopper-Pearson) two-sided 95% CI by study arm at Days 8, 15, 29, 36, 43, 57, 180, 187, 194, 208, and 360 (Table 19 and Table 20).

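### SAP Tables 21–24 keep subjects who cannot seroconvert in the seroconversion denominator, and the primary 4-fold endpoint has two definitions that differ for those same subjects

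*SAP*

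**What the plan says.** **Seroconversion.** SAP 3.3 defines it as a move from negative (A/C.O. below 0.9) to positive (above 1.1). A borderline sample is retested in duplicate and is reported as indeterminate if both retests are borderline. The footnotes to Tables 21 and 23 fix the starting point at the pre-dose 1 sample. The same tables define the denominator as "n=Subjects with results at visit", and Tables 22 and 24 repeat the formats for the PP population. SAP 6.1 bases percentages on non-missing data. The mITT definition in SAP 6.3.1 has no serostatus condition.

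**4-fold rise (primary immunogenicity endpoint).** SAP 3.3 sets the criterion at IgG of at least 0.154 "in a subject that was HEV seronegative at baseline". SAP 4.5.2 and Protocol 7.2.2 say the same with Day 1 as the reference. The primary endpoint, SAP 8.1 and the Table 19 footnote ask only for a rise of at least 4-fold over baseline or pre-dose 1. SAP 8.1 reports it with an "exact (Clopper-Pearson) two-sided 95% CI by study arm".

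**Entry and timing.** Inclusion criterion 6 requires negative HEV IgG and IgM at screening. Sera from enrolled subjects, Day 1 included, go to the laboratory for assay "beginning with the completion of the Day 360 visit".

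**Screening age.** Protocol 5.1 states: "Screening for eligible subjects must be performed within 28 days before Day 1". Protocol 6.2 and Appendix A note f nevertheless provide for laboratory screening older than that, in which case "the subject must have safety laboratories repeated", with details left to the Manual of Procedures (MOP).

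**The concern.** A percentage should count failures only among subjects who could have succeeded. In Tables 21–24, a subject who is not seronegative on Day 1 cannot be in the numerator but remains in the denominator. Because Day 1 serum is assayed after follow-up ends, nobody can notice and act on this at enrollment.

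For the primary endpoint, two programmers could follow the documents faithfully and classify the same subject differently. The study "is not designed to formally test any hypotheses", so these percentages and their intervals are themselves the immunogenicity result. The denominator and the responder rule should be settled before the data are seen.

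**Working it through.** **Inputs.** Vaccine arm: "Given an N of 20 vaccinees" (SAP 5). Interval: Clopper-Pearson, two-sided 95% (SAP 8.1 and 8.2). Value assigned to an IgG-negative sample: 0.0385 Wu/mL, half the lower limit of quantification (SAP 4.5.2, Protocol 7.2.2).

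**1. The plan's own figures.** 4 × 0.0385 = 0.154, which matches the stated threshold. The sample-size table follows 1 − (1 − p)^20 and gives 0.20, 1.98, 18.21, 87.84 and 98.85%, all as printed.

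**2. Where the two 4-fold rules differ.** For an IgG-negative Day 1 sample, set at 0.0385, reaching 0.154 and rising 4-fold are the same event. For a subject who is IgG-positive on Day 1, take a rise from 0.2 to 0.8 as an example. The ratio is 0.8/0.2 = 4, so the subject is a responder under SAP 8.1 and the Table 19 footnote. Under SAP 3.3, SAP 4.5.2 and Protocol 7.2.2 the same subject is not a responder, because the baseline was not seronegative.

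**3. Effect of the denominator on seroconversion.** Let k of 20 vaccinees be non-seronegative on Day 1, and let p be the true rate among the rest. The expected reported rate is p(20 − k)/20, a shift of −pk/20. For k = 1 this is −1/20 = −5 points at p = 100% and −0.80/20 = −4 points at p = 80%. If every seronegative vaccinee converts:

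| k | Kept in denominator | Removed from denominator |
|---|---|---|
| 1 | 19/20 = 95% (75.1–99.9) | 19/19 = 100% (82.4–100) |
| 2 | 18/20 = 90% (68.3–98.8) | 18/18 = 100% (81.5–100) |
| 3 | 17/20 = 85% (62.1–96.8) | 17/17 = 100% (80.5–100) |

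**4. How likely it is.** The documents give no rate of a non-negative Day 1 sample after a negative screen, so this step rests on assumed rates q. With 1 − (1 − q)^20, the chance of at least one such vaccinee is 9.5% at q = 0.5%, 18.2% at 1%, 33.2% at 2% and 64.2% at 5%. The expected number, 20q, runs from 0.1 to 1.0.

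**5. Screening text side by side.** Protocol 5.1 requires screening within 28 days, and criterion 5 requires its listed laboratory values (including glucose, HIV, HBsAg and HCV) within 28 days of enrollment. Protocol 6.2 and note f provide for older screening and name only the safety laboratories for repetition. Protocol 2.3.1 and note f list those as blood count with differential, creatinine and ALT. HEV IgG and IgM appear only in the baseline list. Step 3 does not depend on this, because a screen within the 28 days followed by a borderline Day 1 result is enough.

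**The case against.** A reader might infer that a subject who is not seronegative on Day 1 can never be a responder on the primary endpoint. The documents do not support that. SAP 8.1 and the Table 19 footnote carry no seronegative condition. The restricted definition is attached to a separately named term, 4-fold seroconversion, and can be read as the computing rule for negative samples set at 0.0385. What remains is a conflict to reconcile.

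A reader might also infer that the rescreening rule admits subjects on out-of-date HEV serology. That goes too far as well. Protocol 5.1 still requires screening within 28 days, Section 5 grants no exemptions, and both rescreening passages defer to the MOP, which may add tests. The inconsistency in the text remains.

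Keeping everyone in mITT can be defended as a choice of target, and the downward bias exists only if the target is the rate among seronegative subjects. But the definition of seroconversion itself sets that target.

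Some of the remedy is already planned. Listing 7 gives individual concentrations, Table 15 gives the Day 1 minimum and maximum, and PP removes subjects found ineligible at baseline. These displays would make an unusual Day 1 value visible but would not correct the percentage. PP may not help, because criterion 6 asks for negativity at screening, which such a subject met. Exclusion of previous HEV infection might be invoked, but the SAP does not say so.

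The case is also likely to be rare. Entry requires negative IgG and IgM, recent or planned travel to listed risk areas is excluded, and borderline samples are retested. This stands and limits the importance of the point.

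**Conclusion.** The point holds for seroconversion, a secondary endpoint: Tables 21–24 count as failures subjects who cannot meet the definition. With results from all 20 vaccinees, each such subject costs at most 5 points. When all others convert, one of them moves the lower confidence limit from 82.4% to 75.1%. For the primary 4-fold endpoint, the finding is that the documents hold two definitions. The automatic-failure problem reaches Tables 19–20 only if the seronegative condition is the one intended.

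The size rests on an event whose frequency the documents do not give; 0–1 subjects is the likely range. The late-screening inconsistency is a separate wording matter. The documents do not show that it will put stale HEV serology into the trial. Overall this is a minor but real gap in a descriptive study, worth closing because closing it is nearly free.

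**What to change.** 1. In Tables 21–24, take as the seroconversion denominator subjects who were seronegative on Day 1 for the immunoglobulin class in question and have a result at the visit.
2. Choose one 4-fold definition and use it in SAP 3.3, 4.5.2 and 8.1, Protocol 7.2.2 and the footnotes to Tables 19–20. If the seronegative condition is kept, apply the same restricted denominator there and say whether it refers to IgG alone.
3. Flag in Listing 7 any subject positive or indeterminate on Day 1, and state how mITT and PP handle them.
4. Reconcile Protocol 6.2 and Appendix A note f (repeated in SAP Table 1) with Protocol 5.1 and inclusion criteria 5 and 6, stating whether HEV IgG and IgM are repeated when screening is older than 28 days.

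Items 1–3 cost wording, one flag in a listing and a matching edit to Protocol 7.2.2 if its definition changes. Item 4 is a protocol clarification. It adds a blood test for the few subjects concerned only if the reconciled text calls for one.
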